2. STUDY OBJECTIVES AND ENDPOINTS

2.1. Study Objectives

2.1.1. Primary Objectives

The primary objectives are:

1. To assess the safety and tolerability of one and two administrations of the Bris10 M2SR influenza vaccine each at 10^8 TCID₅₀ delivered intranasally to healthy adult subjects.
2. To assess the safety and tolerability of one and two administrations of the Sing2016 M2SR influenza vaccine each at 10^8 , $10^{8.5}$ and 10^9 TCID₅₀ delivered intranasally to healthy adult subjects

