8. STATISTICAL METHODS AND CONSIDERATIONS

8.1. General Considerations

Prior to the analysis of the study data, statistical methods and table shells will be detailed in a Statistical Analysis Plan (SAP) and finalized before database lock.

The final analysis will be done after the last subject has had the day 57 visit and the data base has been locked. The day 209 data will be included as a supplemental analysis.

Statistical analysis will be the responsibility of Northrim Consulting, Inc, using SAS® (SAS Institute Inc., Cary, NC, USA; version 9.4 or higher).

There are primary, secondary and exploratory objectives, endpoints and analyses. Depending upon the result of the primary and secondary analyses, not all exploratory analyses may be done.

Safety and subject disposition analyses will be conducted on the safety analysis set.

Summarization of primary and secondary efficacy endpoints will be done using FAS. These summaries may be repeated using the PP analysis set.

There are no formal tests of hypotheses in this study. Efficacy outcomes are descriptive only.

The data will be summarized in tables listing the number, mean, standard deviation, median, minimum, maximum, standard error (SE) and a 95% CI of subjects for continuous data, or in tables listing count and percentage for categorical data where appropriate. Tables will be presented by IP treatment and overall. Data listing by subject will be provided.

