8.3.3. Safety Analyses

Safety and tolerability of the Bris10 M2SR and Sing2016 M2SR influenza vaccines as assessed by subject diaries, solicited and unsolicited AEs, vaccine -associated AEs, SAEs, safety labs, vital signs, and physical examinations.

Exposure

Vaccine exposure will be summarized by actual dose, % of expected dose, and % of subjects receiving the expected dose.

Adverse Events

Treatment-emergent AEs (local and systemic) will be summarized as N (%) with AEs, with related-AEs, and by worst severity.

Incidence of TEAEs will be reported by MedDRA-coded SOC, PT and maximum severity.

Incidence of most frequent TEAEs and most frequent treatment-related TEAEs will be reported by SOC and PT

Listings of subjects who died, discontinued the study due to an AE, or experienced an SAE will be provided.

Dose-site reactions will be presented by reaction and severity.

Post-administration of symptoms (memory aid) will be summarized by time point, worst occurrence, and days with symptoms.

Clinical Laboratory Tests

Biochemistry and hematology laboratory results and change from baseline results will be summarized by timepoint using descriptive statistics.

Shift tables of maximum grade compared to baseline tabulated according to the FDA guidance: Toxicity Grading Scale for Healthy Adult and Adolescent Volunteers Enrolled in Preventive Vaccine Clinical Trials, or in accordance with the normal ranges of the clinical laboratory (below, within, or above normal range) for parameters for which no toxicity grades are defined.

A listing of clinical laboratory test results outside the reference ranges will be provided.

Vital Signs

Vital sign results and change from baseline results will be summarized by timepoint using descriptive statistics.

Limited Physical Examination

Abnormal findings in physical examination will be listed.

Pregnancy

A listing of pregnant subjects will be displayed.

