2.1.1.2. Safety Set (SS) Population

The SS Population will consist of all randomized subjects who receive at least one IP administration.

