2.1.1.3. Evaluable Set (EVAL) Population

The Evaluable Set will consist of all randomized subjects who receive both administrations of IP.

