9. PRIMARY OBJECTIVE: SAFETY EVALUATION (SS)

9.1. Extent of Exposure

IP exposure will be characterized by the number of IP administrations received (1 or 2) and N (%) of subjects reported as receiving a complete dose as recorded on the eCRF. Summary statistics will be provided for change in delivery device weights to reflect amount of IP delivered. IP exposure tables will display results by the 5 treatment groups and will be repeated for the SS and the EVAL sets.

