9.2.1. Reactogenicity Assessments: Symptom Memory Aide (SMA)

Fourteen (14) different reactogenicity symptoms (including other/specify) are collected pre-IP administration and once daily for the 7 days following each of the IP administrations via a "Symptom Memory Aide (SMA)", see Protocol Appendix 5. Symptoms are reported by the subject, at 4 levels of intensity (0=None, 1=Mild, 2=Moderate, 3=Severe).

Each symptom will be summarized by severity (worst reported over the course of the 7 days) by treatment and whether subjects experienced a given symptom at any severity. This summary will be done for IP administration 1 and repeated for IP administration 2. Symptom category "other" will be included in the listings only.

Each symptom will be summarized by the number of days with symptoms for each subject. This summary will be done for IP administration 1 and repeated for IP administration 2. Symptom category "other" will be included in the listings only.

Each symptom (and oral temperature) will be summarized by IP administration (1 or 2) and timepoint (Day 1 pre-dose (coded as Day 0), Day 1 post dose, Days 2-7). Summary statistics will be given for oral temperature (mean, SD, median, min, max) and as yes/no (0,1, missing) for each symptom. Symptom category "other" will be included in the listings only.

These summaries will use the EVAL set.

SMA symptoms will not be grouped into local and/or systemic events.

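### Dose 1 symptom-diary reactogenicity is tabulated only in subjects who also received dose 2, so dose-1-only subjects are missing and dose 1 severity rates may be understated

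*SAP*

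**What the plan says.** SAP 9.2.1 plans three summaries of the Symptom Memory Aid: worst severity over the seven days, number of days with symptoms, and symptoms and temperature by timepoint. All three cover each dose; of the first two the SAP says "This summary will be done for IP administration 1 and repeated for IP administration 2", and the third is also split by administration. The section then fixes the population: "These summaries will use the EVAL set".

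The two relevant SAP sets are:

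- SAP 2.1.1.3: "The Evaluable Set will consist of all randomized subjects who receive both administrations of IP".
- SAP 2.1.1.2: "The SS Population will consist of all randomized subjects who receive at least one IP administration".

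Protocol 8.1 states: "Safety and subject disposition analyses will be conducted on the safety analysis set". Protocol 8.3.3 counts the diary as a safety measure, with safety and tolerability "as assessed by subject diaries, solicited and unsolicited AEs, vaccine -associated AEs, SAEs, safety labs, vital signs, and physical examinations", and places the memory-aid summaries under Safety Analyses. The heading of SAP Section 9 carries the Safety Set label. Protocol 8.2 defines no set that requires both doses. SAP Section 12, which lists changes to the planned analyses, does not mention this one.

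**The concern.** The dose 1 tables are conditioned on something that happens about four weeks later, namely receipt of dose 2, and dose 1 tolerability can influence that event. Protocol 7.4 lists a severe AE as a ground on which a subject may be withdrawn, and requires withdrawal when the investigator judges it necessary for safety. The Day 29 exclusions in Protocol 4.2 bar dose 2 after a new prohibited diagnosis or medication. Withdrawn subjects are not replaced (SAP 8.5).

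A primary objective is "To assess the safety and tolerability of one and two administrations of the Sing2016 M2SR influenza vaccine", and there is a matching one for Bris10. One-dose tolerability is therefore a question in its own right, and the SMA tables are the only planned symptom summaries that separate dose 1 from dose 2. If a subject stops after a severe first reaction, the dose 1 table is where a reader would look for it, and it would not be there.

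**Working it through.** The plan states no figure to reproduce. The check has two parts: the set definitions, then an illustration of the possible size.

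**Sets.** Follow a subject who receives dose 1, completes the diary and never receives dose 2.

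| Output | Population | Subject counted? |
|---|---|---|
| AE summaries (SAP 9.2) | Safety Set (Section 9 heading) | Yes, if the symptom was recorded as an AE |
| Exposure (SAP 9.1) | Safety Set and EVAL | Yes, in the Safety Set version |
| SMA tables, dose 1 (SAP 9.2.1) | EVAL only | No |
| SMA tables, dose 2 (SAP 9.2.1) | EVAL only | No, and correctly so |

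The defect is therefore confined to the dose 1 SMA tables. For dose 2, EVAL is simply the set of subjects who received that dose.

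**Size.** In one arm let

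- n = subjects given dose 1 (about 40, from SAP Section 12);
- s = subjects with a severe dose 1 symptom;
- a = those severe reactors who do not receive dose 2;
- b = non-severe subjects who do not receive dose 2.

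Then

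- Safety Set rate = s/n
- EVAL rate = (s − a)/(n − a − b)

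EVAL is lower than the Safety Set exactly when a/(a + b) > s/n, that is, when severe reactors are over-represented among those who miss dose 2.

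The documents give n only. The values of s, a and b below are assumptions. Intervals are exact (Clopper-Pearson) 95%; for 0/m the upper limit is 1 − 0.025^(1/m), for example 1 − 0.025^(1/37) = 9.5%.

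| s | a | b | Safety Set | EVAL |
|---|---|---|---|---|
| 1 | 1 | 0 | 1/40 = 2.5% (0.1 to 13.2) | 0/39 = 0% (0 to 9.0) |
| 2 | 2 | 0 | 2/40 = 5.0% (0.6 to 16.9) | 0/38 = 0% (0 to 9.3) |
| 3 | 3 | 0 | 3/40 = 7.5% (1.6 to 20.4) | 0/37 = 0% (0 to 9.5) |
| 3 | 2 | 0 | 3/40 = 7.5% (1.6 to 20.4) | 1/38 = 2.6% (0.1 to 13.8) |

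Two boundary cases:

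- If everyone receives dose 2 (a = b = 0), both rates are s/n and nothing is lost.
- If those missing dose 2 are all non-severe, the shift is small and upward. With s = 3, a = 0, b = 2, EVAL gives 3/38 = 7.9% against 3/40 = 7.5%.

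**The case against.** The strongest reply is that little is really lost. The primary endpoints (Protocol 2.2.1) count subjects with vaccine-associated AEs or SAEs, and those summaries stay on the Safety Set. SAP 9.2 says investigators were told to record individual symptoms as AEs so that reactogenicity would be captured. A reaction bad enough to stop dosing should then appear in the AE tables and in the listing of discontinuations due to an AE. Disposition shows how many subjects received each dose and tabulates reasons for exclusion from EVAL, and Protocol 8.1 promises by-subject listings. The Section 9 heading is also only a default, since 9.1 uses EVAL beside the Safety Set.

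Most of this stands. The AE output is real mitigation, and Protocol 8.1 is the firmer conflict. It is not a cure: SAP 9.2 also says that a diary symptom need not have been reported as an AE and that the two sources were not reconciled, and no AE summary is planned by dose. Section 9.1 adds EVAL to the Safety Set, whereas 9.2.1 replaces it.

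A reader might infer more than the documents support:

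- **That the rule removes the worst-tolerating subjects as a matter of course.** EVAL drops everyone without dose 2, including for pregnancy or confirmed influenza. A severe AE is only an optional ground for withdrawal, and Protocol 5.9.1 permits common symptomatic medication after dosing. Selective loss is possible, not shown.
- **That a dose-related signal across the Sing2016 levels is flattened.** That needs both intolerance and stopping to rise with dose, and the documents give no data on either. Protocol 1.4.1 reports no severe diary reactions in the first-in-human study, and Protocol 1.4.3 no severe AEs or complaints before challenge in Phase 2a. Those data cover Bris10 up to 10^8 only, so they neither support nor exclude severe reactions to Sing2016.
- **That Day 29 immunogenicity has the same fault.** SAP 8.2 names no analysis set for it.

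**Conclusion.** The point holds for the dose 1 SMA tables. Their population contradicts Protocol 8.1, departs from the SAP's own Section 9 default without being declared, and depends on a later event that the dose 1 outcome can affect. Dose 1 severity rates may be biased downward.

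The actual size cannot be stated, because the number of dose-1-only subjects and their reasons for stopping are not in the documents. The range in the table, 0% shown against 2.5% to 7.5%, is a worst case that assumes every severe reactor stops and no one else does. The partial case gives 2.6% against 7.5%. The effect is nil if all subjects receive dose 2. The primary AE and SAE summaries are not affected.

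**What to change.** In SAP 9.2.1, replace "These summaries will use the EVAL set" with:

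*Summaries for IP administration 1 use the Safety Set; summaries for IP administration 2 use subjects who received the second administration (EVAL).*

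The administration 1 tables may be repeated on EVAL as supportive output, in line with the exposure tables, which SAP 9.1 already plans on both sets. If the sponsor prefers to keep EVAL as the main population for dose 1, SAP Section 12 should declare the departure from Protocol 8.1 and give the reason.

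The cost is one sentence and a change of population flag in the dose 1 table programs. No new data are needed.

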AE/symptom. Therefore, as a secondary presentation, subjects with 3 or more concurrent unrelated AEs of cough, runny nose/rhinorrhea, sneezing, sore throat, itchy throat, itchy eyes, congestion, nasal irritation, hoarseness, headache, body aches/myalgia, tiredness/fatigue, malaise, and fever will have those AEs grouped as URI. This will simplify presentation of the data and is consistent with the protocol.

To facilitate the above reporting standard a total of 15 different AE Preferred Terms (Arthralgia, Cough, Fatigue, Headache, Malaise, Myalgia, Nasal congestion, Nasal discomfort, Nasopharyngitis, Oropharyngeal pain, Paranasal sinus discomfort, Pyrexia, Rhinorrhea, Sinus congestion, or Throat irritation) were considered for contribution to a syndromic diagnosis of URI. Subjects who reported symptoms that resulted in coding of 3 or more of these PTs on a given day, assessed by the Investigator as unrelated to the vaccine, were reported as URI. The severity of the URI was reported as the worst severity of the qualifying AEs considering only days when 3 or more terms were reported. AEs already reported by the Investigator as a URTI were not included in the URI data display.

Targeted physical examinations were conducted throughout the study. PE findings recorded as clinically significant, severe, or life threatening were recorded as AEs. Investigators used their judgement regarding reporting of additional PE findings as AEs.

Clinical laboratory results marked as clinically significant by the Investigator were captured as AEs.

AE's with start dates prior to the first IP administration will be included in the listings, but not in the summaries.

Treatment-emergent AEs (TEAE) are AEs with start dates between administration of the first IP and last IP administration + 30 days. However, if an AE is related to IP then there is no upper bound on the start date. Thus, treatment related TEAEs may have start dates beyond 30 days post IP administration.

All AEs will be coded based on MedDRA (V20.0).

Where provided in Protocol Appendix 1, AEs will be graded according to the Vital Sign and Systemic Toxicity Assessments.

N (%) of subjects with at least one TEAE and N (%) of subjects with at least one treatment-related treatment-emergent AE (TRAE) will be summarized. TEAE and TRAE by worst severity will be summarized. Note that the protocol uses the term "vaccine associated" AEs, but the eCRF collects AEs as related, not related.

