N (%) of subjects with TEAE will be reported by System Organ Class and Preferred Term (SOC/PT) and maximum severity. N (%) of subjects with TRAE will be reported by SOC/PT and maximum severity.

N (%) of subjects with TEAE by SOC/PT by overall frequency (decreasing) will be reported. N (%) of subjects with TRAE will be reported by SOC/PT by overall frequency (decreasing).

All AEs will be included in the listings. Only treatment emergent AEs will be summarized. Separate listings of subjects who died, discontinued the study due to an AE, or experienced a serious AE, if any, will be provided.

No statistical test comparing adverse event rates will be done.

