9.5. Limited and Targeted Physical Examinations

A physical exam to determine the subject's suitability for the study was done prior to IP administration. Limited physical examinations consisting of nasal, lung and throat assessments were done predose, and at 5 and 30 minutes post dose on Days 1 and 29, and at Days 8, 36, 57 and 209. At the discretion of the Investigator, targeted physical examination may have been performed on other body systems and findings may be recorded as AEs. Physical examination findings will be included in the listings.

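### The SAP rules out grouping memory-aid symptoms into local and systemic events, so no summary table shows how many subjects per arm had any local or any systemic reaction

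*SAP*

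**What the plan says.** Protocol 8.3.3 makes two commitments that bear on this point. On adverse events: "Treatment-emergent AEs (local and systemic) will be summarized as N (%) with AEs, with related-AEs, and by worst severity". On the administration site: "Dose-site reactions will be presented by reaction and severity". Protocol Appendix 3 supplies the definition and grading of local reactions for intranasal dosing in three rows: nasal pain or irritation, nasal congestion or rhinorrhea, and bleeding.

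SAP 9.2.1 handles the memory-aid data one symptom at a time: "Each symptom will be summarized by severity (worst reported over the course of the 7 days) by treatment". This is done after the first administration and again after the second, with further tables of days with symptoms and of symptoms by timepoint. The section ends by stating that "SMA symptoms will not be grouped into local and/or systemic events".

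SAP 9.2 counts subjects with any treatment-emergent event and any related event, then breaks these down by MedDRA term: "N (%) of subjects with TEAE will be reported by System Organ Class and Preferred Term (SOC/PT) and maximum severity". It has no local, systemic or dose-site category. For grading it cites Protocol Appendix 1 (vital signs and systemic symptoms) and not Appendix 3.

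SAP section 12, which records changes to the planned analyses, covers early closure of enrollment, telephone visits and assay data not yet available. It does not mention this point.

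**The concern.** The study takes Sing2016 M2SR into humans for the first time, at three dose levels given by nasal spray. A basic tolerability question is how many subjects in each arm had any local reaction, how many had any systemic reaction, and how bad the worst one was. That is a count of subjects. Symptoms overlap within a subject, so a row for congestion and a row for runny nose do not add up to it.

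The protocol appears to promise a local and systemic presentation and defines what local means. The SAP rules out the grouping for the memory aid, offers no substitute in the adverse event tables, and does not say that anything was dropped. A reader of the study report would have to work through by-subject listings to obtain a figure that one table row could give.

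**Working it through.** There is no stated figure to reproduce. The group size was chosen empirically and nothing is formally tested. The check has two parts.

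**1. Does any planned summary table contain the count?**

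| Planned in Protocol 8.3.3 | SAP output | Match |
|---|---|---|
| Memory-aid symptoms by timepoint, worst occurrence and days | 9.2.1: all three, per symptom and per administration | Yes |
| Dose-site reactions by reaction and severity | No output of that name; 9.2.1 gives irritation, bleeding, runny nose and congestion separately by worst severity | Largely, in substance |
| Treatment-emergent events, local and systemic, as N (%) by worst severity | 9.2: any event, any related event, SOC/PT; no local or systemic row | Overall counts only |
| Abnormal examination findings listed | 9.5: listed | Yes |

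The adverse event tables do not close the gap. They group by MedDRA class, not by the Appendix 3 definition. SAP 9.2 also says that a memory-aid symptom may or may not have become an adverse event, and that the two sources were not reconciled. Pooling across terms within a subject is not foreign to this SAP: section 9.2 combines three or more concurrent unrelated terms into an upper respiratory infection for a secondary display.

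**2. Can the count be derived from the single-symptom tables?**

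Inputs: about 40 subjects per group (SAP section 12). The four memory-aid symptoms matching Appendix 3 are irritation, bleeding, runny nose and congestion. Symptom rates are assumptions; the documents give none.

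For symptom rates p1 to p4, the proportion with at least one symptom lies between max(p) (complete overlap) and min(1, sum of p) (no overlap). With all four at 20%:

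- Lower bound: 0.20, and 0.20 × 40 = 8 subjects.
- Upper bound: 4 × 0.20 = 0.80, and 0.80 × 40 = 32 subjects.
- If independent: 1 − 0.8⁴ = 0.59, and 0.59 × 40 ≈ 24 subjects.

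Other assumed rates:

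| Congestion / runny nose / irritation / bleeding | Any local, lower to upper |
|---|---|
| 5 / 5 / 5 / 2% | 5% to 17% |
| 10 / 10 / 10 / 2% | 10% to 32% |
| 20 / 20 / 15 / 5% | 20% to 60% (8 to 24 of 40) |
| 30 / 30 / 20 / 5% | 30% to 85% |

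The same bounds apply to counts at or above any given intensity, so the worst-severity split is not recoverable either.

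For scale, if the count were reported, its exact 95% interval would run from 9.1% to 35.6% for 8/40 and from 43.3% to 75.1% for 24/40. The latter is 75.1 − 43.3 = 31.8 percentage points wide. The range left open by unknown overlap is 80 − 20 = 60 points in the equal-rates example and 60 − 20 = 40 points for 20/20/15/5%. In these examples, not tabulating the count loses more information than the small sample does.

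**The case against.** Much can be said for the SAP, and most of it stands.

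- The sentence at issue concerns memory-aid symptoms. On those, the SAP delivers what Protocol 8.3.3 asks, and the protocol never expressly promises to group them.
- The dose-site commitment is worded reaction by reaction, so the per-symptom tables largely meet it. Mainly the label is missing.
- The parenthesis about local and systemic events can be read as scope (both kinds are included) and not as an order to tabulate them apart. The departure from protocol is therefore arguable.
- The primary endpoint, subjects with vaccine-associated events, is fully reported in SAP 9.2.
- Protocol 8.1 plans by-subject listings, so the count could be assembled by hand.

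Three stronger readings are tempting, and the documents do not support them.

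- A reader might infer that local reactogenicity goes unreported. It does not: each nasal symptom is tabulated by arm, administration and worst intensity.
- A reader might infer that a dose trend across the three Sing2016 levels is hidden. The bounds describe overlap within one arm. A symptom that rises with dose would show in its own row. A trend would be concealed only if every symptom rate stayed flat while the overlap changed, and nothing suggests that.
- A reader might infer that the nose, throat and lung examinations are never compared across arms. SAP 9.5 does say "Physical examination findings will be included in the listings", but Protocol 8.3.3 plans a listing as well. Moreover, "PE findings recorded as clinically significant, severe, or life threatening were recorded as AEs", investigators could report other findings, and all of these enter the event tables.

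What the objection does not remove is the plain fact that the SAP rules out a subject-level tolerability summary and the remaining tables cannot supply it.

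**Conclusion.** The point holds as a gap in descriptive reporting. No summary table gives the number of subjects per arm with any local, any systemic or any solicited memory-aid reaction, and none can be derived from the planned rows. That conclusion rests on the SAP's text and on the bounds, which hold whatever the true rates. The illustrated size (8 to 32 of 40) rests on assumed rates of 20% and would be narrower if symptoms were rare: 5% to 17% in the lowest scenario above.

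It deserves correction because tolerability is a primary objective and the data are already collected. It does not threaten the primary endpoint or the validity of any planned comparison. Whether it is also a departure from protocol depends on how the local and systemic wording in 8.3.3 is read. On either reading, section 12 should make the position clear.

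**What to change.** In SAP 9.2.1, replace the sentence with a table giving, for each administration and treatment group, N (%) of subjects by worst intensity over the 7 days with:

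- any local symptom, using the Appendix 3 terms: nasal irritation, nasal bleeding, runny nose, stuffy nose/congestion;
- any systemic symptom: feverish, tiredness, body/muscle aches, joint pain, body rash, headache, nausea, vomiting;
- any solicited symptom.

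Assign sore throat and cough to one group in advance and move them to the other in a sensitivity grouping. Name the symptoms individually: SAP 9.2.1 counts 14 including the free-text category, while Appendix 5 names 14 before it. State the denominator too, because for the existing memory-aid tables "These summaries will use the EVAL set", which leaves out subjects who received only the first administration.

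In SAP section 12, record any part of Protocol 8.3.3 that is still not delivered, with the reason. A by-arm table of examination findings would be a useful option but does not correct a departure.

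The cost is SAP wording and one table from existing data. The downside is that placing throat symptoms and cough is a convention. Timing matters for that choice: the protocol allows the sponsor to be unblinded after Day 57, and SAP 8.6 allows top-line results by treatment before lock. Taking the local list from Appendix 3, which is already in the protocol, leaves little room for a data-driven choice. For throat symptoms and cough, document when the choice was made and by which role.
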